4.10 Meal test

After an overnight fast, a liquid meal will be provided matching the macronutrient content of the prevailing diet and amounting to 30% of the estimated daily calorie requirements for weight maintenance as determined by 1.6×REE measured at screening. Blood samples will be obtained at 0, 10, 20, 30, 60, 90, 120, 180, 240, 300, and 360 minutes to measure glucose, lactate, free fatty acid, triglyceride, C-peptide, and insulin concentrations. Blood samples for research will also be collected.

4.11 Continuous Glucose Monitoring (CGM)

Subjects will wear FDA-approved CGMs during their inpatient admission except during the MRS procedure. The devices will be used to record glucose in real-time, approximately every 5 minutes. The system consists of a small sensor, transmitter, and hand-held receiver (about the size of a pager). The small sensor, with a small needle attached, will be inserted subcutaneously. The transmitter, which is attached to the sensor, will send the measured glucose to the receiver. The data stored in the receiver will be uploaded to a software for analysis. We will calibrate the device using fingerprick blood glucose meter measurements. After initial calibration, the system will require blood glucose calibrations twice a day. Sensors expire after 7 days, so a new one will be inserted at the beginning of each inpatient week.

4.12 MRI/MRS

The subject will lie supine in the MR gantry and will be asked to hold their breath during scans. The duration will depend on their tolerance. The MR imaging test will be performed in collaboration with another NIH investigator. Subjects will undergo the MRI/MRS after signing a separate informed consent document specific to the imaging study (protocol 11-DK-0168). This separate imaging study consent also involves CT scan. However, the CT scan portion is optional and refusal to undergo CT scan will in no way affect participation in the current study. MR spectroscopy will be performed primarily for assessment of hepatic fat content. Each MRI scan will last no more than 2 hours. Gadolinium, a contrast agent sometimes administered to enhance visualization of the heart and blood vessels, will not be used during MR study scans. Subjects with hearing loss that may be affected by the MRI or metal implants that are incompatible with MRI (e.g., pacemakers, metallic prostheses such as cochlear implants or heart valves, shrapnel fragments, etc.) will be advised to not participate in the MRI/MRS procedures.

4.13 Saliva Collection

Variation in basic taste receptor genes (sweet, salty, sour, bitter, and umami) and nutrient sensing genes may contribute to differences in food preferences and dietary patterns. The taste receptor genes and their variants will be chosen accordingly for sweet and umami (T1R [taste receptor, type 1]), bitter (T2R [taste receptor, type 2]), and salty (ENaC [epithelial sodium channel][26]). The saliva sample will be collected using Oragene® (Genotek, Kanata, Canada) and used for the isolation of genomic DNA. Genomic DNA samples will be used as a template in TaqMan® assays (Applied Biosystems, Foster City, CA) in duplicates. Genotyping will be done by investigators blind to any subject information. Samples will be stored in a -80 °C freezer. For genotype quality assurance, the concentration of DNA in stored samples will be checked using a Nanodrop® Spectrophometer ND100 prior to use. The observed genotypes will be checked for Hardy–Weinberg equilibrium. The exploratory analysis will investigate the relationship of taste and obesity-related genotype with dietary intake, and with sweet and salt preference and

thresholds. An analysis of variance will test whether taste detection thresholds or preference differ by genotype. Saliva collection takes approximately 2 minutes to complete. This procedure will be conducted at the end of the study period.

4.14 Psychophysical Taste Task: Sucrose and Salt Detection Thresholds

Sucrose and salt detection thresholds will be assessed using a two-alternative forcedchoice staircase procedure was developed at the Monell Center for Adults [27-29]. The twoalternative forced choice is a psychophysical method developed to elicit responses about an individual's experience regarding a stimulus. It focuses on the evaluation of a single attribute (e.g., sweetness or saltiness), and the stimulus is adjusted based on the individual's responses [30, 31]. For this study, all testing will take place in a private, comfortable room. Subjects will be fasted for at least one hour before the task and acclimate to the testing room and to the researcher for approximately 15 minutes before testing. For the first trial and each subsequent trial, subjects will be presented with pairs of solutions in random order; within each pair, one solution will be distilled water, and the other will be the taste stimulus. Subjects will be instructed to taste the first solution presented within the pair, swish the solution in their mouth for 5 seconds, and expectorate. This will be repeated for the second solution within the pair. Between solutions, subjects will rinse their mouth with water; they will rinse once within a pair, and twice between successive pairs. After tasting both solutions within a pair, subjects will be asked to point to the solution that has a non-neutral taste. A tracking grid will be used to record subjects' responses [32-34]. This method eliminates the need for a verbal response and has been shown to be an effective method for assessing both taste and olfaction in children [32, 35]. The task takes approximately 60 minutes to complete. Participants will complete this task at the end of each test diet period.

4.15 Psychophysical Taste Task: Sucrose and Salt Preference

Sucrose and salt preference will be assessed using a two-series paired comparison-tracking method developed at the Monell Center for Adults [27-29]. Subjects will be presented with pairs of solutions differing in sucrose concentration (3, 6, 12, 24, and 36 g per 100 mL) and salt (0.92–6.14% wt/vol NaCl). They will be asked to taste the solutions without swallowing and point to which of the pair they liked better. Subsequently, each pair presented will be determined by the subject's preceding preference choice. The entire task is then repeated with the stimulus pairs presented in reverse order. After completion of the taste task, the geometric mean of the sucrose and salt concentrations chosen will be determined. This serves as an estimate of the participant's most preferred level of salt or sucrose [35, 36]. The task takes approximately 30minutes to complete. Participants will complete this task at the end of each test diet period.

4.16 Above-threshold or Suprathreshold intensity

Subjects will be trained on the use of the general labelled magnitude scale (gLMS) before we measure perceived intensities. Two trials consisting of 4 ascending concentrations of each stimulus (sucrose, NaCl) with the first "concentration" being water will be presented to the subjects. All four concentrations will be presented in random order without repeat. Subjects will rate the perceived intensity of the stimulus using the gLMS scale and mean intensities of the two trials at each concentration for each stimulus to evaluate subjects' taste intensity perception. We will use 0.00, 0.09, 0.35, and 1.05 mol/l sucrose solutions and 0.00, 0.056, 0.18, and 0.56 mol/l salt solutions.

4.17 Computerized Behavioral Tasks

Some of the assessments below may be completed multiple times across the participant's inpatient stay to assess any effect of diet.

Slips of Action Paradigm. Goal-directed behaviors are guided by the assessment and valuation of possible outcomes. Thus, if the outcome of a certain behavior is devalued, the behavior is less likely to be performed. Habit responding occurs when an individual's actions are driven by external stimuli, which trigger and automatic behavioral response. This task assesses such learning in three stages: control discrimination training, congruent discrimination training, and an incongruent conflict task. In the initial stage if subjects respond correctly to the cue box instructions they will receive a reward.

For the second stage, no feedback will be provided for correct or incorrect responses. This stage of the task should be controlled predominantly by a goal-directed system. The third stage features a conflict between the previously associated cues and outcomes. The total task time will be 27 minutes.

Reward Prediction Error. A computerized probabilistic procedural learning task, the Probabilistic Selection Task, to assess participants ability to learn from both positive and negative outcomes. Dopamine plays a key role in reinforcement learning. Learning from positive outcomes is thought to be a result of phasic bursts firing of dopamine which stimulates the D1R direct ("Go") pathway and inhibits the D2R indirect pathway ("Stop"). The dip in dopaminergic firing experienced as a result of negative outcomes is thought to support learning to avoid the unrewarded choice. This task trains participants on reward contingencies and then tests their learning strategy to determine whether they are more adept at learning predominantly from positive feedback (suggestive of high phasic dopamine response) or from negative outcomes (suggestive of sufficient degree of dip in phasic and tonic dopamine response). Both phases of the task combined last approximately 25 minutes.

Liking and Wanting. Subjects will complete the Liking and Wanting computer assessment. The liking and wanting procedure comprises two tasks designed to assess (1) explicit liking and wanting, followed immediately by (2) implicit wanting for the same target food stimuli [43, 44]. The separate task elements will be integrated to fully randomize explicit and implicit trials. Experiment generator software (E-prime v2.0) is used to integrate the single stimulus trials for the liking task with the paired stimuli trials for the wanting task. Food stimuli presented in the procedure are selected from a database of photographic stimuli and sorted according to their fat content and taste properties into one of four separate categories: high-fat savory (HFSA); low-fat savory (LFSA); high-fat sweet (HFSW); and low-fat sweet (LFSW). Each category is represented by four different foods; hence a total of 16 different food stimuli will be presented in the procedure.

The aim of the explicit task is to obtain introspective hedonic measures for the same stimuli used in the implicit wanting task. Therefore, each food stimulus is assessed independently using visual analogue scales (VAS). The explicit computer task trials consist of 16 food stimuli presented one at a time and rated according to a 100-mm VAS anchored at each end by the statements "not at all" and "extremely". Subjects will be prompted with the statements "How pleasant would it be to taste some of this food now?" and "How much do you want some of this food?" Responses on

the software will be recorded online and mean ratings for each food category (HFSA, LFSA, etc.) are automatically computed.

Implicit wanting is measured by a behavioral "forced choice" methodology. In this task, a food stimulus from one of the four food categories is paired with one stimulus from the remaining categories to form a series of 96 trials in which the subjects will be given the standardized instruction to select the food they "most want to eat now". In addition to recording the frequency of selections made in each category (with a possible range of 0–48), which may reveal a relative preference, reaction time (in milliseconds) of each choice is also measured. By covertly recording reaction time, subjects will be unaware of implicit changes in their behavior on the task, while remaining free to determine the direction of their choices.

Delay Discounting. People generally prefer immediate rewards over delayed rewards, even when the delayed reward has a higher value. The degree to which delayed rewards are discounted in comparison to immediate rewards may provide an index of impulsive decision-making. It has been reported that obese individuals may have difficulty adhering to diets because the long-term rewards of weight loss are strongly discounted when compared to immediate rewards, such as palatable food [45].

We will implement delay discounting computer procedures using an image of a food that scored highly on each individual's liking scale. This food image will be presented along with a forced choice statement such as "Would you rather eat this food now or receive \$10 tomorrow?" The subject must select either the "food" or "money" option. We will also measure how long it takes to make each selection. The same food image will always be used as the hypothetical subject-specific reward, but hypothetical monetary choices will vary in the amounts of: \$1, \$5, \$10, \$20, \$50, \$100 and the associated delay times will vary from: now, 4 hours, tomorrow, 1 week, 2 weeks, and 1 month.

Experiment generator software (E-prime v2.0) will be used to present the paired stimuli trials and will be programmed to center the cursor between each trial to produce more consistent response times.

4.18 Daily Ketone Measurements

We may measure daily blood levels of beta-hydroxybutyrate using a hand-held device with a small quantity of blood (about 20 $\mu L)$ obtained by capillary sampling. We may also measure breath acetone levels using a handheld breathalyzer. Daily urine samples for ketone measurements may be collected. These measurements will allow for estimating the kinetics of onset and dissipation of nutritional ketosis when subjects transition to and from the low carbohydrate diet.

4.19 Fecal sampling for Microbiome Analyses

Fecal samples will be collected in sterile cryovials and will be stored at -80°C until DNA extraction during the admission. If available, fecal samples will be collected at least once during each diet period.

5. Statistical Analysis

Day to day variability of *ad libitum* energy intake has a standard deviation of about 500-600 kcal/d [37-39]. Therefore, over a 14-day diet period each subject will have a mean energy intake with a standard error of about 130-160 kcal/d and the mean energy intake difference between the study diets will have a standard error of about 190-230 kcal/d. Over the final 7-day diet period, each subject will have a mean energy intake with a standard error of about 190-230 kcal/d and the mean energy intake difference between the study diets will have a standard error of about 270-320 kcal/d. Using the conservative assumption that within-subject energy intake correlations are zero, the 20-subject study cohort will have an 80% power to detect a difference in mean *ad libitum* energy intake between the diets of about 125-150 kcal/d using the full 14-day period for each diet and about 175-210 kcal/d comparing the final 7 days of each diet period with a Type I error probability of 0.05.

Previous *ad libitum* diet studies comparing mean energy intake between 14 day periods consuming diets differing in macronutrient content have observed differences >250 kcal/d [11, 12] which is greater than the minimum detectable difference for a 10-subject cohort under the same assumptions as above. Therefore, the 20-subject cohort of our study is adequately powered to detect physiologically significant differences in *ad libitum* mean energy intake between the diets.

6. Safety Considerations

6.1 Possible Risks and Hazards

Research-related risks in this study include those associated with study procedures, namely blood drawing, indirect calorimetry, respiratory chamber, doubly labeled water, measurement of body composition by dual energy x-ray absorptiometry (DXA), wearing physical activity monitors, continuous glucose monitoring, oral glucose tolerance testing, and measurement of liver fat by MRS. There are no study medications. A decrease in blood glucose is an expected outcome of eating a low carbohydrate diet and hypoglycemia is a possible risk, especially during the low-carbohydrate diet period. We will closely monitor all subjects throughout the study using twice daily fingerstick glucose measurements. If their blood glucose is <60 mg/dl and is associated with hypoglycemic symptoms (headache, dizziness, and shakiness) the Licensed Independent Practitioner (LIP) will be notified. Snacks will be given from the protocol snack bin and blood glucose will be checked in 15 minutes, and the procedure will be repeated until the blood glucose is 60 mg/dl or the participant is asymptomatic. If the blood glucose is <40 mg/dl, the test will be repeated and STAT blood glucose level will besent to the laboratory for verification. Fifteen grams of fast acting carbohydrates will be provided to the subject immediately and the process will be repeated every 15 minutes until the blood glucose level increases to 60 mg/dl or the symptoms subside. If hypoglycemia is recurrent or severe, we may choose to withdraw the participant from the study.

Blood drawing. The placement of intravenous needles may cause transient pain, and may also result in bruising, bleeding, and/or clotting at the site of needle insertion. A medical provider will be available should any of these problems occur. There is a possibility that a catheter placement would be unsuccessful or need to be removed. If this should occur, another catheter would be placed. The approximate volume of blood to be drawn for research purposes (including the screening visit) is 500 ml according to the schedule below.

Screening Visit	Diet 1	Diet 2	Total
10 ml	256 ml	244 ml	500 ml

This blood volume is within the NIH guidelines for limits of blood drawn for research purposes (550 ml in any 8-week period). Participants will be informed that they should not have other research blood sampling or provide a blood bank donation during any 8-week period that includes the study period.

Oral Glucose Tolerance Test. Subjects may experience faintness, nausea, and vomiting after taking the glucose solution.

Indirect calorimetry. The use of the ventilation hood may cause some minimal discomfort in claustrophobic subjects.

DXA. The amount of radiation during the DXA scan is less than one mrem to the whole body. This radiation exposure is below the guideline of 5000 mrem per year allowed for research subjects by the NIH Radiation Safety Committee The use of the DXA scan apparatus may cause some minimal discomfort in claustrophobic subjects and may cause some minimal back pain in a small minority of the individuals.

Doubly labeled water. Rapid administration of double-labeled water can rarely be associated with mild and transient dizziness. At the doses being administered in this protocol, this side effect is unlikely to occur.

Respiratory chamber. Besides inconveniences that can reasonably be expected as a result of spending an extensive time (24h) in the live-in room calorimeter, there is no risk to subjects' physical health. Claustrophobia is an exclusionary criterion. All subjects will be given an opportunity to experience the metabolic chamber prior to enrollment in the study.

Profile of mood states questionnaire. There is no known risk associated with the POMS questionnaire, however, there is the potential of subjects finding completing the task tedious or some may find the questions probing and too personal in nature to comfortably answer. Subjects will be informed that they do not have to respond to all the questions if they have reservations about sharing such personal information.

DSM-5 Self-Rated Level 1 Cross-Cutting Symptom Measure. There is no known risk associated with this self-report measure. However, there is the potential of discovering clinically relevant information requiring further follow-up. If this is the case, a member of the research team will contact the subject, and appropriate follow up will be planned.

Food frequency questionnaire. There is no known risk associated with the FFQ.

Three-factor eating questionnaire. There is no known risk associated with the TFEQ.

MacArthur Socioeconomic Status (SES) Questionnaire. There are no known risks associated with the MacArthur SES questionnaire although some subjects may find completing the task tedious or some may find the questions probing and too personal in nature to comfortably answer. Subjects will be informed that they do not have to respond to all the questions if they have reservations about sharing such personal information.

Hunger and satiety assessment. There are no known risks associated with the hunger and satiety assessment

Sensory and palatability assessments. There are no known risks associated with the sensory and palatability assessment.

Self Reported Habit Index. There are no known risks associated with the sensory and palatability assessment.

Satisfaction with life, Happiness and Well Being scales. There are no known risks associated with the sensory and palatability assessment.

UPPS-P Impulsive Behavior Scale (UPPS-P). There is no known risk associated with the UPPS-P.

Liking Survey. There is no known risk associated with the liking survey.

Barrett Impulsiveness Scale (BIS). There is no known risk associated with the BIS.

Yale Food Addiction Scale 2.0 (YFAS 2.0). There is no known risk associated with the YFAS 2.0.

Physical activity monitors. There are no risks associated with the monitors, but subjects may find them to occasionally be inconvenient.

Continuous Glucose Monitoring System. According to the device manufacturer, there is minimal risk associated with the device. Possible side effects include but are not limited to local infection, inflammation, pain or discomfort, bleeding at the insertion site, bruising, itching. Because this protocol represents the first use of this device by our research team, we do not know the frequency of such complications of the device. A medical provider will be available should any of these problems occur.

MRI/MRS. There is a small chance of claustrophobia or muscle-skeletal discomfort from lying partially in the magnet. During the imaging measurement, the noise may be somewhat unpleasant, but ear plugs will be provided for comfort. Although the long-term risk of exposure to a magnetic field is not known, the possibility of any long-term risk is extremely low from the information accumulated over the past ten years.

MRS Warning: Certain implants, devices, or foreign objects implanted in the human body may interfere with the MR procedure. Volunteers who have undergone specific prior surgeries (i.e. heart, brain, gastric bypass, breast augmentation, etc) and/or have implants of specific types may be required to provide their IMPLANT CARD in order to determine implant safety/compatibility with the magnet before a scan is performed. The continuous glucose monitor will be removed prior to the MRS procedure.

Saliva collection for taste genotyping. This is a non-invasive procedure and there are no risks associated with saliva collection. There are no known clinical consequences of variations in the taste receptor genes that will be studied. Information regarding genetic results will not be shared with the participants.

Psychophysical taste task: Sucrose and Salt Detection Thresholds. There are no risks associated with assessments of taste detection thresholds.

Psychophysical taste task: Sucrose and Salt Preference. There are no risks associated with assessments of taste preference.

Above-threshold or Suprathreshold intensity: There are no risks associated with assessments of taste preference.

Slips of Action Paradigm: There are no risks associated with the Slip-of-Action paradigm assessment.

Reward prediction error: There are no risks associated with the Reward Prediction Error assessment.

Liking and Wanting: There are no risks associated with the Liking and Wanting assessment.

Delay Discounting: There are no risks associated with the Delay Discounting assessment.

Daily ketone measurements: According to the device manufacturer, there is minimal risk associated with the device. Possible side effects include but are not limited to local infection, inflammation, pain or discomfort, bleeding at the insertion site, bruising, itching. Blood ketones are expected to be low ≤0.6 mmol/L but may be higher (up to 1.5mmol/L) under fasting conditions, during exercise vigorously or when the person is ill. If a person is ill and has a blood ketone measurement of >1.5mmol/L, a confirmatory blood sample will be sent to the NIH CC lab and the medical provider notified.

Stool Sampling: Stool sampling is not associated with any health risk but may be uncomfortable for some participants.

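### The stopping rule for glucose below 40 mg/dl can be read as letting treatment end on symptom relief while glucose is still below 40 mg/dl

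*Combined protocol and SAP*

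**What the plan says.** Section 6.1 names hypoglycaemia as a possible risk, chiefly on the low-carbohydrate diet, and sets out two steps.

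- **Below 60 mg/dl.** This step needs symptoms as well as the reading. Where the reading "is associated with hypoglycemic symptoms (headache, dizziness, and shakiness) the Licensed Independent Practitioner (LIP) will be notified". Snacks are given and glucose is rechecked after 15 minutes, "until the blood glucose is 60 mg/dl or the participant is asymptomatic".
- **Below 40 mg/dl.** "If the blood glucose is <40 mg/dl, the test will be repeated", and a STAT sample goes to the laboratory to verify the value. Rapid carbohydrate, 15 g, is given at once, and the cycle runs again at 15-minute intervals. Its stated end is "until the blood glucose level increases to 60 mg/dl or the symptoms subside". No symptom condition is attached to the opening of this step, and it has no notification clause of its own.

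Routine surveillance is also in Section 6.1: "We will closely monitor all subjects throughout the study using twice daily fingerstick glucose measurements". It adds a discretionary exit from the trial: "If hypoglycemia is recurrent or severe, we may choose to withdraw the participant from the study". Section 4.11 has participants wear a continuous monitor that records about every 5 minutes. On the use of those readings it says: "The data stored in the receiver will be uploaded to a software for analysis".

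**The concern.** This is the plan's written response to its lowest glucose range. A participant enters the step on a glucose value but can be released from it on symptoms alone. Easing symptoms do not show that glucose has recovered, yet the rule accepts them in place of a glucose value.

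At stake is the safety of an individual participant during a rare event. The 15 g dose is the only rescue in the plan specified as rapidly acting carbohydrate. Under Section 3.3.2, snacks follow the diet being eaten, so they are a weaker carbohydrate source in the low-carbohydrate period, where the plan expects most of the risk.

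**Working it through.** No design figure is involved in the main point, so the check is one of logic. A short calculation on the cost of the remedy follows.

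**1. The stop rule at a 15-minute recheck.** As written, stop = (glucose at least 60) *or* (symptoms subsided). The last two columns show the two possible corrections.

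| Glucose (mg/dl) | Symptoms | As written | Symptom exit deleted | Symptom exit barred below 40 |
|---|---|---|---|---|
| 60 or more | present | stop | stop | stop |
| 60 or more | gone | stop | stop | stop |
| 40–59 | present | continue | continue | continue |
| 40–59 | gone | stop | continue | stop |
| below 40 | present | continue | continue | continue |
| below 40 | gone | **stop** | continue | continue |

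The last row is the problem. At that exit the shortfall from the plan's target is more than 60 − 40 = 20 mg/dl.

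**2. Two readings of how the below-40 step starts.**

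- *Escalation of the symptomatic below-60 step.* The participant had symptoms, so the practitioner has been notified. The last-row exit is permitted outright.
- *Glucose alone.* A recheck below 40 meets the opening condition again, so treatment is required; the symptom condition says the cycle may end. The text supports both. For a participant who never had symptoms, it is unclear whether any repeat is required, and no practitioner notification is written. By contrast, the ketone paragraph of Section 6.1 does write in notification of the medical provider for an ill participant above 1.5 mmol/L.

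**3. Does anything else supply a glucose floor?**

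- The below-60 step does not: it starts only with symptoms and itself ends when they are gone.
- The STAT sample gives a further value. No separate action is written for its result, although a laboratory value below 40 could be read as meeting the opening condition again.
- The continuous monitor has no stated alarm or action threshold.
- The fingersticks are twice daily, with no stated spacing and no link to the stop rule.
- Follow-up of abnormal results (Section 6.2), medical oversight (Section 6.4) and withdrawal (Sections 6.1 and 9) set no stopping value.

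**4. Exposure.** Over 28 days, 20 completers have 20 × 28 × 2 = 1,120 scheduled fingersticks, of which 20 × 14 × 2 = 560 fall on the low-carbohydrate diet. This counts opportunities, not events. The documents give no event frequency.

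**5. Could longer treatment disturb the primary outcome?** Assume 4 kcal/g, that rescue doses count as intake, and that one participant receives 1 to 4 extra doses, all within the comparison window of one diet. One dose is 15 × 4 = 60 kcal. The shift in the 20-subject mean difference is then:

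- 14 days: 60/(14 × 20) = 0.21 kcal/d for one dose and 0.86 for four. Against the plan's smallest detectable difference of 125 kcal/d (Section 5, taken as stated), 0.86/125 = 0.7%.
- Final 7 days: 60/(7 × 20) = 0.43 kcal/d for one dose and 1.71 for four. Against 175 kcal/d, 1.71/175 = 0.98%.

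**The case against.** The best defence is that the below-40 sentence is a standing condition: any recheck below 40 starts the step again, so nobody is released at that level. That is a fair reading if glucose alone is the trigger, and it means the text there is contradictory rather than plainly permissive. It does not rescue the escalation reading. Nor does it remove the need to edit, since an instruction that both requires and ends treatment should be settled.

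A reader might infer that the plan clearly permits stopping below 40 however it is read, or that such a participant would go unobserved until the next fingerstick. The documents support neither. The first dose, the repeat test and the STAT sample are always required, a laboratory value is still to come, and the monitor is recording. On the reading where the exit is clearest, the practitioner has already been notified. What remains is that none of these has a stopping value written into it.

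It is also fair to say that events should be rare. Participants are inpatients without diabetes, take no drugs that influence metabolism and have snacks all day. That lowers the severity but leaves the wording as it is.

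A last objection is that requiring 60 mg/dl goes further than the stated harm, because it extends dosing to participants without symptoms at 40–59, a state the plan does not otherwise treat. This is correct, and it is why a narrower alternative is offered.

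**Conclusion.** The point stands as a defect of safety wording. The symptom condition has no glucose floor and no other section supplies one, so the rule can be followed to a stop below 40 mg/dl. On the escalation reading this is permitted; on the glucose-alone reading the text conflicts with itself and leaves out notification for a participant without symptoms. The conclusion rests on the written text, not on how unit staff would probably act.

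Severity is low. No event rate can be derived from the documents, and rarity is a judgement from the eligibility criteria and the inpatient setting. A reader might infer some threat to the trial's results, but nothing in the documents links this rule to the endpoints, the power calculation or the analysis.

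**What to change.** 1. In the below-40 step of Section 6.1, delete the symptom alternative so that the cycle ends only when a repeat glucose has reached 60 mg/dl. At minimum, state that easing symptoms cannot end the step while glucose is below 40.
2. Do not simply change *or* to *and*. That would keep dosing someone at or above 60 with a lingering headache, and it is undefined for someone who never had symptoms.
3. State that the Licensed Independent Practitioner is notified of any reading below 40 mg/dl, with or without symptoms.
4. The below-60 step can stay as it is. The Medically Accountable Investigator should choose between the two versions in item 1 and confirm the wording.

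The cost is one phrase removed and one clause added, plus at most a few extra 15-minute rechecks and 15 g doses per event. With the 60 mg/dl version, some of those doses go to participants without symptoms at 40–59 mg/dl. Under the assumptions above, the effect on measured intake is below 1% of the plan's smallest detectable differences.
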